#### III. Objectives and Endpoints

The primary aim of this study is to determine whether distributing 100 U of onabotulinumtoxinA over less injection sites (three) is just as effective as common practice (ten).

Our secondary aim is to assess whether less injection sites has fewer complications (UTI/ hematuria) and leads to better patient satisfaction and tolerability as this procedure is done in the office while the patient is awake.

We hypothesize that a 3-site injection method is as effective as a 10-site method and will lead to higher patient satisfaction. The primary outcome will be incontinence episodes per day assessed at 3 months after BTX injection. Secondary outcomes will include voiding symptom scores and voiding diary parameters as measured by the Overactive Bladder Questionnaire-Short Form (OABq-SF), International Consultation on Incontinence Questionnaire-Short Form (ICIQ-SF), Global Response Assessment (GRA), Visual Analog Scale (VAS) on the day of injection to assess for pain, satisfaction, and tolerability, and 3-day voiding diaries to be completed throughout the study.

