Consent to send out pre-screening activities may be done by telephone script with all elements of information sheet included. Participant agreement is consent to send prescreening activities. Once the participant is present for enrollment visit, a formal consent will be performed for study participation. Informed consent will be obtained from all patients prior to conducting any study activities. Consented patients will complete the OAB-g SF, ICIQ-SF, 3-day voiding diary and enrollment guestionnaire (demographics, medical history, concomitant medications, etc.) prior to study enrollment. A urinalysis (UA) will be collected at this visit as well and a urine culture (UCx) will be performed, if necessary. If the patient meets the eligibility criteria, they will be randomized (1:1) into the 3-injection site group or the 10injection site group. We plan on performing a stratified randomization so the number of BTX naïve and previous BTX responder patients will be equivalent in both arms in order to minimize selection bias. Patients will be blinded to the number of injections they will receive. Adverse events and concomitant medications will be assessed at each follow-up visit. A diary will also be completed, collected and reviewed at each follow-up visit. GRA will also be gathered at each follow up visit. Visual Analog Scores will be gathered at the end of the injection visit to assess for patient satisfaction, pain, and tolerability.

Patients will be asked to remain off any oral anticholinergic or beta-3 agonist medications, PTNS therapy, or any neuromodulation throughout the entirety of the study.

Patients will follow up two weeks post-injection (±7days) for an office visit. OAB-q SF, GRA, ICIQ-SF, 3-day voiding diary, UA and post void residual (PVR) will be collected. If necessary, a UCx will be ordered for evaluation.

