At 3, 6, 9, and 12 months post-injection (± 14 days), patients will return for follow-up appointments. OAB-q SF, GRA, ICIQ-SF, patient satisfaction, 3-day voiding diary, and UA will be collected. If necessary, a UCx will be ordered for evaluation. We will also assess for adverse events and concomitant medications at each of these visits. Specific adverse events we will be tracking include urinary retention (inability to void), elevated PVR of greater than 300 cc, UTI, excessive bleeding at injection sites that requires cautery, and systemic BTX effects (systemic weakness). If at any visit the patient is found to have a UTI, they will be prompted to repeat that visits questionnaires and 3-day diary at an unscheduled visit once the prescribed UTI treatment has been completed. At the unscheduled visit AEs will be reviewed and a clinical decision will be made by an investigator if UTI symptoms are still present after treatment completion. The unscheduled visit will occur at the urology research clinic.

If a repeat botox injection is given at the 3, 6, or 9 month visit, the subject will have a 2 week follow up visit identical to visit 3 in the schedule of events before continuing to be followed every 3 months.

While in-person visits are preferable, if the patient is unwilling or unable to attend a study visit (specifically visits 4-7) they will not be withdrawn from the study. In order to assess patient safety and provide continuing follow-up, the patient may be contacted by phone and/or mail. If necessary, study information may be collected by either or both of these methods; phone (current medications, AE assessment) and/or mail (questionnaires, voiding diary). If a patient requires a remote visit, they may complete at least one, but not all visits remotely.

	Consent and Screening	Enrollment and Treatment	2 Weeks Post-BTX Visit (±7 days)	3 Months Post-BTX Visit d (± 14 days)	6 Months Post-BTX Visit d (± 14 days)	9 Months Post-BTX Visit d (± 14 days)	12 Months Post-BTX Visit (± 14 days)
	Visit 1	Visit 2	Visit 3	Visit 4	Visit 5	Visit 6	Visit 7
Consent	X						
Eligibility	X						
Demographics, Medical History	X						
OABq-SF ICIQ-SF	X		X	X	X	X	X
3-day Voiding Diary	X		X	X	X	X	X
Urinalysis, Urine Culture as needed	X	X	X	X	X	X	X
Pregnancy test before injection as needed a	X	X		X	X	X	
Post void residual (PVR) ♭			Х				
BTX injection		X					
Repeat BTX				X	X	X	

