The patient will receive BTX injections according to the group to which they have been randomized. If the patient has been randomized into the 3 injection group, they will receive an additional 7 "sham injections" with the needle retracted (no break in the mucosa). We decided on this as a sham treatment instead of actually puncturing the mucosa without injecting BTX because the point of our study is also to assess patient satisfaction and tolerability as well as rates of adverse events (ie hematuria and UTI). In order to do this, we want to puncture the mucosa less (3 vs 10). For the 3 injection group, every 3rd injection will be an actual mucosal penetration and injection (for 3 total injections containing BTX) in order to keep the patient blinded as best as possible. The 3 BTX injections will still be placed in the location as outlined in the diagram (Figure 1). The other 7 injection's will be verbally emphasized by the clinician but will not have mucosal penetration with the needle. It has been our experience that patients have variable sensation with needle penetration, sometimes no or minimal sensation to a clear sensation of a needle poke. The provider will verbalize the injection number to the patient whether it is a true injection or not in order to keep a believable pace. All patients will be told "This is injection #1. This is injection #2. This is injection #3." and so forth. Care will also be taken to prevent the patient from seeing the syringe so they cannot guess the arm of the study to which they were randomized. All patients will think they are receiving ten injections. Post-injection, the patient will be evaluated for hemostasis. Cautery will be used if deemed necessary by the physician. If hemostasis is achieved, this will conclude the visit.

If at the 2 week follow-up the patient has an elevated post-void residual (PVR) <350cc and is symptomatic or if the patient has a PVR > 350 cc and is non-symptomatic, the patient may be placed on either clean intermittent catheterization (CIC), one time straight catheter with close follow-up or indwelling foley catheter. Management for elevated post void residual

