#### VIII. Data Safety Monitoring Plan

Ongoing safety monitoring will be performed by the study staff, including the Principal Investigator (PI) and co-investigators. The PI will have ultimate responsibility of assuring patient safety. Safety issues will also be addressed in the annual reports to Beaumont's Investigational Review Board (IRB).

Additional data safety monitoring procedures include:

- Research Administration's Clinical Research Quality and Process Improvement Program (CRQIP) will perform in-house monitoring of the first patient enrolled after the completion of visit 1
- An audit of the study records after the first 10 patients are enrolled and at the half way point of enrollment by Urology Research Nurse that is not directly involved with the research study. This will be done to ensure the safety of patients and lack of significant adverse effects. Additional auditing may occur, as needed.
- Throughout the study all adverse effects will be reported to the research nurse and then to the PI at the time of the event. Adverse events, serious adverse events, and unanticipated problems not listed in the risks section of this protocol will be reported per IRB guidelines.

Once 25 patients have been randomized to each arm, we will assess the efficacy/futility of BTX injections based on the 3-month follow-up visit data.

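### Hematuria is a named secondary outcome, but it has no definition, standard question, time window or named comparison, and the only bleeding event specifically tracked is cautery

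*Combined protocol and SAP*

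**What the plan says.** **The aim.** Section III states: "Our secondary aim is to assess whether less injection sites has fewer complications (UTI/ hematuria". These are the only two complications it names.

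**The design.** The Injection Procedure section explains why the seven sham injections leave the mucosa intact. The study is also meant to assess satisfaction, tolerability and "rates of adverse events (ie hematuria and UTI", and it continues: "In order to do this, we want to puncture the mucosa less (3 vs 10".

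**The tracked events.** Section IV reads: "Specific adverse events we will be tracking include urinary retention (inability to void), elevated PVR of greater than 300 cc, UTI". The list then adds "excessive bleeding at injection sites that requires cautery" and systemic toxin effects. Hematuria is not on it. On when cautery is decided, the Injection Procedure section says: "Post-injection, the patient will be evaluated for hemostasis. Cautery will be used if deemed necessary by the physician".

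**General capture.** Section IV also says: "Adverse events and concomitant medications will be assessed at each follow-up visit". The schedule marks adverse events at Visits 2 to 7 and urinalysis at every visit. Section VIII adds: "Throughout the study all adverse effects will be reported to the research nurse and then to the PI at the time of the event".

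**The analysis.** Section VII makes adverse events, as a class, a secondary endpoint. It does not mention hematuria.

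**The concern.** The plan shaped its sham partly around a comparison of hematuria, yet it never turns hematuria into a measured variable. The one bleeding item it singles out is an intervention at the end of the procedure, so it says nothing about blood that a patient notices later at home. Cautery is also the physician's decision, and whoever delivers 3 or 10 punctures must know the arm.

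That leaves general adverse event reporting. A comparison between arms needs the same question put in the same way to everyone. The plan describes blinding of patients only and does not say whether the staff who assess adverse events are blinded. If probing or recording differs by arm, the hematuria rates will differ for that reason alone. If mild bleeding is recorded haphazardly in both arms, a result of no difference cannot be interpreted. Neither fault can be repaired at the analysis stage, because the events were never collected in a standard way.

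**Working it through.** **1. What the plan supplies for a hematuria comparison**

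| Needed | In the documents |
|---|---|
| Named as an outcome | Yes: section III, and the sham rationale |
| On the list of specifically tracked events | No |
| Definition (visible or microscopic, reported or by urinalysis) | None |
| Same question for every patient | None stated; adverse events are assessed, method not given |
| Time window | None |
| Named comparison | None; section VII refers only to adverse events |

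**2. Can an existing item stand in?**

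- *Cautery*: judged at the injection visit, so it cannot cover later bleeding.
- *Urinalysis*: the first one after injection is at 14 ± 7 days, that is days 7 to 21, so earlier transient bleeding can be missed. No rule turns blood on urinalysis into an event. The Injection Procedure section also allows injection of asymptomatic patients whose dipstick already shows blood, so later blood is not necessarily new.
- *Retreatment rule* (section IV): it refers to patients who have hematuria, which shows the event is expected but does not define or solicit it.

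**3. The plan's own sizing, reproduced**

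Inputs from section VII: 0.85 in both arms, margin 0.15, one-sided 0.025, power 80%.

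n per arm = 2 × 0.85 × 0.15 × (1.960 + 0.842)² / 0.15² = 88.95, rounded up to 89. This matches the plan (178 in total). There is no sizing for hematuria to reproduce.

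**4. Expected cases**

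Section V lists blood in the urine at 1% to 10%, with no rate by arm. 89 × 0.01 = 0.9 and 89 × 0.10 = 8.9, so about 1 to 9 cases per arm.

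**5. Power at 89 per arm**

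Rates by arm and a two-sided 0.05 test are assumptions. The formula is Φ[(d − 1.960 × SE0) / SE1], with SE0 pooled and SE1 unpooled.

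For 10% against 3%, the mean rate is 0.065:
- SE0 = √(2 × 0.065 × 0.935 / 89) = 0.0370
- SE1 = √((0.10 × 0.90 + 0.03 × 0.97) / 89) = 0.0366
- Power = Φ[(0.07 − 1.960 × 0.0370) / 0.0366] ≈ 47%

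| Ten-site vs three-site rate (assumed) | Expected cases | Power, full capture |
|---|---|---|
| 10% vs 5% | 8.9 vs 4.5 | 24% |
| 10% vs 3% | 8.9 vs 2.7 | 47% |
| 10% vs 1% | 8.9 vs 0.9 | 75% |
| 5% vs 1.5% | 4.5 vs 1.3 | 26% |
| 1% vs 0.3% | 0.9 vs 0.3 | 8% |

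For 10% against 3%, 80% power would need 194 per arm. The normal approximation is rough at such small counts, but the picture is clear.

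**6. Effect of capture (capture fractions are assumptions)**

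- *Incomplete but even.* With 10% vs 3% true, power falls from 47% at full capture to 37% at 75% and 26% at 50%.
- *Uneven, no true difference.* With 10% true in both arms, 75% captured in one and 50% in the other: 8.9 × 0.75 = 6.7 against 8.9 × 0.50 = 4.5 recorded cases. The gap is purely an artefact.
- *Uneven, true difference.* With 10% vs 3% true, 50% captured in the ten-site arm and all in the three-site arm: 4.5 against 2.7. The true gap of 8.9 − 2.7 = 6.2 cases shrinks to 1.8.

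**The case against.** The strongest reply is that the tracked list is introduced with the word include, so it is not exhaustive. Adverse events are assessed at every follow-up visit, all adverse effects go to the research nurse and then the PI, and adverse events are a secondary endpoint. Hematuria is therefore recordable and falls within a planned comparison. This stands. A reader might infer from the list that cautery is the only bleeding that will be captured, or that later bleeding is recorded only if a patient volunteers it. The documents do not support either inference: they say adverse events are assessed, without saying whether by open question, checklist or prompt, and no CRF is among them. A reader might also call cautery a rarer event than hematuria, but no cautery rate is given.

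A second reply is that low power comes mainly from the sample size and not from poor capture. That also stands: most scenarios in the table are underpowered with every event recorded. It would be wrong to say that a finding of no difference must reflect poor capture.

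A third is that this is a clarification of one secondary safety outcome that leaves the primary test untouched. The second half is true. But a missing collection standard is more than missing detail, because it has to be in place before patients are seen.

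**Conclusion.** The point holds in a limited form. Hematuria is a stated secondary outcome and part of the reason for the sham, but the plan gives it no definition, no standard question, no window and no named comparison, and neither cautery nor urinalysis as planned can replace them. Hematuria data would not be absent; they would be unstandardised, with a risk of incomplete or uneven capture.

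The size is modest. About 1 to 9 cases per arm are expected from the plan's 1-10%, and at counts this low a few missed events matter. Power is about 47% for 10% against 3% with full capture, so the comparison is descriptive with or without the fix. The rates by arm, the two-sided 0.05 level and the capture fractions are assumptions; the documents give none of them. What the fix buys is valid and even ascertainment, not adequate power. The primary endpoint and the 178 patients are unaffected. The change should be made, because it is nearly free and cannot be made after the data are in.

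**What to change.** 1. Add hematuria to the specifically tracked events in section IV.
2. At the 2-week visit after each injection, ask every patient the same question: was visible blood seen in the urine since the injection (yes/no), and on how many days. This visit already follows every injection, and the patients answering are blinded.
3. In section VII, name the answer after the first injection as the hematuria comparison, reported as the rate in each arm with a confidence interval for the difference, and state that it is descriptive.
4. Keep cautery as a separate procedural event.
5. Do not count blood on urinalysis as a new event when the pre-injection dipstick was positive for blood.

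**Cost.** One CRF question at existing visits, and more mild events recorded in both arms. The sample size, treatment and primary analysis do not change.

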#### **Schedule of Research Activities**

Injection							
GRA			Х	X	X	Х	X
VAS		Х		Xe	Xe	Xe	
Concomitant	Х	Х	Х	Х	Х	Х	Х
Medications							
Adverse events		Х	Х	Х	Х	Х	Х

a If the patient has the potential to be pregnant (ie. pre-menopausal and/or no surgical history of hysterectomy/oophorectomy), a pregnancy test will be checked prior to all BTX injections.

b If the PVR is elevated at 2 week follow-up appointment, additional follow up for management of elevated PVR will be at the discretion of the provider (see below for definition and additional detail).

c Repeat injections will be offered at the clinician's discretion. Patients will be eligible for repeat injections 3 months after initial injection. Patients will be allowed to undergo repeat injections at a minimum of a 3 month interval. Injection will not be offered at the 12 month visit as this is the final study visit.

d If a patient is re-injected with Botox they will have a 2 week follow-up visit during which, time, the same activities as shown in visit 3 will be conducted.

e If patients request a repeat BTX injection, a VAS questionnaire will be performed post injection.

#### **Injection Procedure**

The injection procedure consists of injections of 100 U for IDO at 3 or 10 injection sites. The BTX will be reconstituted at a concentration of 10 U per 1 cc as is common practice. For example, a 100 U dose will be diluted with 10 cc of injectable saline. The diagram below shows the injection sites at the bladder base (just beyond the trigone). The procedure requires local lidocaine anesthesia only.

Figure 1. 3- and 10- site cystoscopic injection locations are outlined in the bladder.

Pre- and post-procedure antibiotics will be given at the discretion of the provider. After a negative urine analysis or if a patient has a positive dipstick (positive leukocyte esterase

and/or positive nitrites and/or positive blood) but is asymptomatic for a UTI, will proceed with Botox injections at the clinicians discretion. The patient's urethra will be prepped with betadine and 50 ml of 1% liquid lidocaine plain will be instilled, via catheter, into the patient's bladder and left for 10 minutes.

A flexible cystoscope will be used for the in-office procedure. This will be sterilized per standard office procedure between uses. A one-time use, Laborie injeTAK®, 23-gauge cystoscopic injection needle will be utilized as this is the needle used in both practices. The needle is retractable and can be adjusted to 0, 2, 3, 4, and 5 mm lengths. The needle will be extended out to 3 mm. Bladder wall thickness is dependent on the condition of the patient's bladder as well as degree of distention. Based on the literature, average bladder wall thickness on ultrasound of patients with OAB ranges from 4 to 6 mm. This can of course vary with degree of distention. Based on these findings, and in conjunction with previously mentioned MRI findings of nearly 20% extravasation using a 4 mm needle depth, we opted for a 3 mm needle depth.

Additionally, a recent meta-analysis showed no difference in efficacy or safety according to depth of injection (suburothelial vs. intradetrusor). Based on these findings, we will leave it up to the surgeon to decide between suburothelial or intradetrusor injections. This data, however, will be collected for analysis at the end of the study.

The patient will receive BTX injections according to the group to which they have been randomized. If the patient has been randomized into the 3 injection group, they will receive an additional 7 "sham injections" with the needle retracted (no break in the mucosa). We decided on this as a sham treatment instead of actually puncturing the mucosa without injecting BTX because the point of our study is also to assess patient satisfaction and tolerability as well as rates of adverse events (ie hematuria and UTI). In order to do this, we want to puncture the mucosa less (3 vs 10). For the 3 injection group, every 3rd injection will be an actual mucosal penetration and injection (for 3 total injections containing BTX) in order to keep the patient blinded as best as possible. The 3 BTX injections will still be placed in the location as outlined in the diagram (Figure 1). The other 7 injection's will be verbally emphasized by the clinician but will not have mucosal penetration with the needle. It has been our experience that patients have variable sensation with needle penetration, sometimes no or minimal sensation to a clear sensation of a needle poke. The provider will verbalize the injection number to the patient whether it is a true injection or not in order to keep a believable pace. All patients will be told "This is injection #1. This is injection #2. This is injection #3." and so forth. Care will also be taken to prevent the patient from seeing the syringe so they cannot guess the arm of the study to which they were randomized. All patients will think they are receiving ten injections. Post-injection, the patient will be evaluated for hemostasis. Cautery will be used if deemed necessary by the physician. If hemostasis is achieved, this will conclude the visit.

If at the 2 week follow-up the patient has an elevated post-void residual (PVR) <350cc and is symptomatic or if the patient has a PVR > 350 cc and is non-symptomatic, the patient may be placed on either clean intermittent catheterization (CIC), one time straight catheter with close follow-up or indwelling foley catheter. Management for elevated post void residual

(PVR) will be at the discretion of the provider. If the patient is a clinical non-responder by 3 months follow-up, subsequent management will be at the clinician's discretion. These patients will be followed, and data will be collected. We plan on conducting an intent to treat analysis which will identify any subject not assessed at 3 months after the first BTX injection as a treatment failure. However, patients who are clinical responders by 3 months and have return of symptoms will be eligible for retreatment. If patients undergo re-treatment, they will continue to receive the same number of injections they originally received. In other words, if they were originally randomized into the 3 injection arm, they will receive 3 injections at retreatment.

After any retreatment, patients will have a 2 Week Follow-up visit before continuing to be followed every 3 months. Findings of an elevated PVR will be addressed as stated above.

If the patient had systemic BTX effects the patient will not be offered repeat injections. If they have hematuria, UTI(s), or temporary urinary retention, they can be offered retreatment at the patient and clinician's discretion.

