#### Data analyses

A biostatistician will perform all statistical analyses using SAS or similar statistical software. Descriptive statistics will be calculated. A completer analysis will be conducted for those who finish the study per protocol. The primary endpoint will be assessed comparing incontinence episodes per day at 3 months after BTX injection. This comparison will also be made for all other visits using t-tests or chi-square tests, as appropriate.

Secondary endpoints will include adverse events and comparisons between 3-site and 10-site groups looking at the GRA responses between 3-site and 10-site groups at 3 months (± 14 days) post injection, 3-day voiding diary and OABq-SF and ICIQ-SF at 3 months (± 14 days) post-injection. We will also compare post-injection VAS scores to assess for tolerability, satisfaction, and pain. Changes from baseline will also be analyzed. This comparison will also be made for all other visits using appropriate statistical tests.

In addition to a completer analysis, we also plan on conducting an intent to treat analyses which will identify any subject not assessed at 3 months after the first BTX injection as a treatment failure. In order to assess for all possible situations, 4 different scenarios will be run: 1) All dropouts will be considered non-responders for both groups 2) All dropouts will be considered responders for both groups, 3) Dropouts in the BTX 10 group will be considered responders and those in the BTX 3 group, non-responders, and 4) Dropouts in the BTX 10 group will be considered non-responders while those in the BTX 3 group, responders.

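### Antibiotic choice is not kept independent of the arm, although UTI is a named comparison, so prescribing that differs by arm could bias that comparison in either direction

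*Combined protocol and SAP*

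**What the plan says.** - **Antibiotics.** Section IV, Injection Procedure: "Pre- and post-procedure antibiotics will be given at the discretion of the provider". No rule there or elsewhere ties the decision to anything other than the provider's judgement.
- **Blinding.** Section IV, Methodology: "Patients will be blinded to the number of injections they will receive". No other party is said to be blinded. In the 3-site arm the operator carries out seven sham injections with the needle retracted, and "The provider will verbalize the injection number to the patient whether it is a true injection or not".
- **UTI as an outcome.** Section III: "Our secondary aim is to assess whether less injection sites has fewer complications (UTI/ hematuria". The Injection Procedure gives the same interest as a reason for a sham that does not puncture the mucosa: the study is also meant to assess tolerability "as well as rates of adverse events (ie hematuria and UTI". Section IV lists UTI among the tracked adverse events, and Section VII, Data analyses, says: "Secondary endpoints will include adverse events and comparisons between 3-site and 10-site groups".
- **What is recorded.** Section IV: "Adverse events and concomitant medications will be assessed at each follow-up visit". The schedule marks concomitant medications at all seven visits, including Visit 2. Section VII plans no summary of antibiotic use by arm.

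**The concern.** Antibiotics are given to lower the risk of infection. If their use depends on the arm, the UTI comparison mixes the effect of the number of punctures with the effect of the prescribing. Section II suggests that fewer sites may lower UTI rates. A provider who shares that view could cover 10-site patients more often, which would hide a real benefit of the 3-site method. The opposite pattern would create an apparent benefit. Blinding the patient gives no protection, because the patient does not make the choice.

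UTI is one of the two complications named in the secondary aim, so the bias would fall on a comparison that the trial set out to make. It could not be repaired afterwards: once enrolment is over, nobody can reconstruct what the provider would have prescribed without knowing the arm.

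**Working it through.** **1. The plan's own figure.** The only sample size stated is for the primary endpoint (Section VII: success 0.85 in both arms, margin 0.15, one-sided alpha 0.025, power 80%). n per arm = (1.960 + 0.842)² × (0.85×0.15 + 0.85×0.15) / 0.15² = 7.85 × 0.255 / 0.0225 ≈ 89. This agrees with the plan and does not depend on antibiotics. No sample size or power is given for UTI.

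**2. Who knows the arm, and when.** The operator performs either ten true injections or three true and seven sham, so the operator knows the arm once injecting. A post-procedure choice made by the injector is therefore made with knowledge of the arm. For pre-procedure antibiotics the text leaves the matter open: Section IV places randomisation after eligibility is confirmed, the schedule has no line for randomisation, and nothing says when the provider learns the result.

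**3. Size of a possible bias.** Inputs:
- b, the UTI risk without antibiotics: assumed 12%, 15% or 20%. Section V (risks of the injection procedure) says only that UTI occurs more than 10% of the time.
- RR, the risk ratio with antibiotics: assumed 0.4 or 0.6.
- u, the share given antibiotics: assumed 60% vs 80%, or 50% vs 90% (3-site vs 10-site).
- No true effect of the number of sites.

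UTI rate in an arm = b × (1 − u × (1 − RR)), so the spurious difference = b × (1 − RR) × (u10 − u3).

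Across all 12 combinations this runs from 0.12 × 0.4 × 0.2 = 1.0 point to 0.20 × 0.6 × 0.4 = 4.8 points. In eight of them, however, the 10-site rate falls below 10%; in the 4.8-point case it is 0.20 × (1 − 0.9 × 0.6) = 9.2%. Four combinations keep it above 10%:

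| b | RR | Use, 3 vs 10 sites | UTI, 3 sites | UTI, 10 sites | Spurious difference | 95% half-width, 89 per arm |
|---|---|---|---|---|---|---|
| 15% | 0.6 | 60% vs 80% | 11.4% | 10.2% | 1.2 points | 9.1 points |
| 20% | 0.6 | 60% vs 80% | 15.2% | 13.6% | 1.6 points | 10.3 points |
| 20% | 0.4 | 60% vs 80% | 12.8% | 10.4% | 2.4 points | 9.4 points |
| 20% | 0.6 | 50% vs 90% | 16.0% | 12.8% | 3.2 points | 10.3 points |

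Half-width = 1.96 × √[(p3(1 − p3) + p10(1 − p10)) / 89]. Last row: 1.96 × √[(0.1344 + 0.1116) / 89] = 10.3 points.

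Exchanging the two use figures reverses the sign. The 10% check then bites less, because the 10-site arm is the one with fewer antibiotics. Seven combinations pass, and the spurious advantage for 3 sites runs from 1.2 to 4.8 points (the largest being 9.2% vs 14.0%, half-width 9.4 points).

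**4. Effect on a true benefit.** Take b = 20%, RR = 0.6 and a true halving with 3 sites; two-sided 0.05 is assumed, since no UTI test is specified. With 50% use in both arms the rates are 8.0% vs 16.0%, a difference of 8.0 points with 37% power. With 30% vs 70% use they are 8.8% vs 14.4%, a difference of 5.6 points with 21% power. Without any imbalance, power to detect a halving from a rate of 10% to 30% is only 24% to 67%.

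**The case against.** The case on the other side has several sound parts.

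- A reader might infer that every antibiotic choice is made with knowledge of the arm. The documents do not support that. It is certain only for post-procedure choices made by the injector.
- A reader might infer that 10-site patients will be covered more often. Nothing in the documents shows that prescribing will differ at all, and the prescribing gaps and risk ratios above are assumptions.
- A reader might take 4.8 points as the size of the likely penalty on the 3-site arm, or call the bias as large as a plausible real benefit. That 4.8-point case needs a 10-site UTI rate of 9.2%, below the frequency in Section V. That section does not say whether its figure was observed with antibiotics, so this is a plausibility check and not a proof.
- The assumed bias lies well inside sampling error at 89 per arm. UTI has no stated test, alpha or power and is one item within adverse events.
- Concomitant medications are already collected, so an imbalance could be seen and reported.
- Provider discretion is a deliberate choice, and no two sections contradict each other on it.

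All of this limits the certainty and the size. It does not remove the point. Seeing an imbalance does not undo it, and antibiotic use chosen after allocation is a post-randomisation variable, so adjusting for it does not fully restore the comparison that randomisation gives. Low power means that the UTI estimate will be imprecise, which is no reason to leave an avoidable bias in it.

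**Conclusion.** The point holds as a risk of bias in a secondary comparison. The plan leaves antibiotics to provider discretion, does not separate that decision from knowledge of the arm, and compares UTI between arms. The direction is open and the size cannot be derived from the documents. If the 10-site arm receives more antibiotics, the assumed inputs consistent with a 10-site UTI rate above 10% give a spurious difference of about 1 to 3 points against the 3-site arm. Under the reverse pattern the same inputs allow a somewhat larger shift in its favour. Either is smaller than the sampling error of 9 to 10 points in those cases. A modest imbalance with a weak antibiotic effect would matter little.

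The documents do not support a claim that unequal prescribing will occur, that pre-procedure choices are made with the arm known, or that the primary result is compromised. The primary sample size of 89 per arm is unaffected. The change is worth making because it is cheap and can only be made before patients are treated.

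**What to change.** Keep provider discretion and fix the order of steps at Visit 2:

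1. The provider records the planned pre- and post-procedure antibiotics on the Visit 2 form before the allocation is opened.
2. Any later change is logged with its reason.
3. Section VII adds a table of planned and actual antibiotic use by arm.
4. Section VII defines the main UTI comparison as the period after the first injection and before any re-injection. Re-treated patients keep their original number of sites, so the provider may already know the arm when antibiotics are next chosen. The length of this period can differ between arms, so follow-up time should be shown by arm.

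The cost is one form field, a fixed sequence and a slightly less flexible workflow on the injection day. Changes after allocation remain possible, so the bias is reduced and made visible but not eliminated. The fix does not touch how UTI is ascertained: cultures are taken only when judged necessary and no case definition is given, which is a separate route to bias. No antibiotic regimen is proposed.
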